6.5 Postprocedure Assessments and Care

Immediately postprocedure, a nasal assessment (visual and endoscopic exam) for each nostril including endoscopic video will be conducted prior to discharging the participant and reported on the Study Procedure eCRF.

Participants will be asked to indicate the pain level experienced during the study procedure from anesthesia delivery to procedure completion using the VAS pain score instrument on the Pain VAS CRF.

At the discretion of the study physician, the following care may be provided and should be documented:

- Use of nasal saline spray and antibiotic ointment 2 to 3 times daily for 1 week.
- The participant should be instructed not to manipulate the treatment site (i.e., no nose blowing) for 24 hours with the exception of any necessary hemostasis.
- Remind participant to continue to hold all anticoagulants for 3 days post procedure.

Participants should have their first study follow-up visit (1 week +/- 3 days) scheduled within the visit window prior to release.

Participants should not receive other concomitant nasal treatment therapies (other than those specified above) or interventions after the procedure through the 36-month follow-up to avoid confounding the evaluation of the effect of the treatment, unless the additional care is in response to an adverse event or is considered in the best interest of the participant. Should a treatment or procedure be in the best interest of the participant, it must be documented in the source. The participant will remain in the study and be followed through 36 months. Concomitant nasal treatments will be monitored at follow-up evaluations.

6.6 Follow-up Evaluations and Study Exit

Follow-up visit dates will be calculated from the study procedure date (Day 0). Follow-up visits should be scheduled within the specified visit windows described in the Schedule of Events (Section 6.1) and Table 1 (Section 9.3.2). An in-office follow-up evaluation is scheduled for 1 week and 13 weeks (3 months) after the procedure. In addition, follow-up evaluations at 26 weeks (6 months), 52 weeks (12 months), 104 weeks (24 months) and 156 weeks (36 months) after the treatment procedure will be conducted remotely as a telephone assessment by site personnel. The timing of all follow-up evaluations is based on the date of the procedure and should not be altered based on the actual time of preceding follow-up visits. Participants who make non-study visits should be evaluated for possible adverse events and an Adverse Event Report eCRF should be submitted if appropriate.

All participants should be followed through the final follow-up evaluation at 156 weeks (36 months) postprocedure regardless of their earlier success/failure classification. Every effort should be made to avoid having participants withdraw

Clinical Study Protocol – SWELL Study

from the study (Section 10.6). If a participant does choose to withdraw from the study, it is very important to record information regarding the reason(s) and the last known status of the participant.

The following assessments will be conducted as indicated for each follow-up time points and recorded on the Follow-up Visit eCRF:

In-office evaluation - 1 Week:

- Nasal assessment (visual and endoscopic exam) for each nostril including endoscopic video.
- Current use and any change in use of medication.
- VAS for pain score (completed by participant).
- Adverse events.

In-office evaluation - 3-month (13 Weeks):

- Nasal assessment (visual and endoscopic exam) for each nostril including endoscopic video.
- Review of current use and change in use of medication for symptoms of nasal obstructions.
- NOSE Scale score (completed by participant).
- NRS ease of breathing score (completed by participant).
- SNOT-22 (completed by participant).
- CT imaging (Substudy – selected sites only).
- Participant Satisfaction Survey (completed by participant).
- Adverse events.

Remote evaluations - 6-month (26 Weeks), 12-month (52-Weeks), 24-month (104-Weeks) and 36-month (156-Weeks) follow-up:

- Current use and participant-reported change in use of medication, and other therapies for symptoms of nasal obstruction and participant-reported changes in frequency of use.
- NOSE Scale score (verbal administration by site personnel).
- NRS ease of breathing score (verbal administration by site personnel).
- SNOT-22 (verbal administration by site personnel).
- Participant Satisfaction Survey (verbal administration by site personnel).
- Adverse events (study staff follow-up required if participant indicates an event).

Study exit:

Participants meeting the study requirements as planned will be exited from the study upon completion of the 36-month follow-up evaluation. If a participant reaches the 36-month follow-up evaluation and is experiencing a new or ongoing adverse event, the study sponsor should be contacted to discuss the need and/or methods for continued surveillance of the event.

Study exit applies to those participants where data is no longer collected for a study participant. A Study Exit form should be completed and entered into the electronic data capture (EDC) Systems in the following cases:

- Completion of 36 month participant questionnaires
- Signed consent but no procedure took place (eg, screen failure)
- Participant was unable to complete the follow-up visits
- Withdrawal of informed consent
- Physician exited participant based on medical or surgical necessity or other reason
- Participant received treatment outside of the study that, in the opinion of the investigator, would affect the study results.
- Lost to follow-up (3 attempts should be made and documented in the participant's record indicating due diligence by the site)
 - If a participant misses a questionnaire window and cannot be contacted, the participant may remain in the study, as contact may be re-established for a future questionnaire window period. (Any missed study assessment is considered a protocol deviation.) Participant withdrawal should be reported within 5 days of site becoming aware. participant death should be reported within 24 hours to Aerin Medical.
- Participant Death

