Other Outcome Measures:	Adverse Events - Incidence (type and category) of adverse events overall and by follow-up interval. Nasal Assessment - The target SSB within each nostril will be visually assessed at screening, prior to the procedure, immediately after the procedure, and 3 months after the procedure. The use of an endoscope for visual assessment is required. Representative endoscopic video of each nasal passage will be captured for each assessment. Endoscopic nasal assessment will include assignment of an SSB grading score. ³⁶ CT Assessment - A subset of study sites will be selected to participate in a substudy of the use of computed tomography (CT) imaging to assess changes in the SBB after treatment. Radiographic changes, including change in size of the SSB, will be assessed using CT imaging prior to the procedure and at 3 months after the procedure.
	NOSE Scale Score: 
• Mean and mean change from screening at the 3-, 6-, 12-, 24- and 36-month follow-up evaluations.• Distribution of NOSE Scale score severity categories (mild, moderate, severe, extreme) at the 3-, 6-, 12-, 24- and 36-month follow-up evaluations.

Clinical Study Protocol – SWELL Study

- Mean, change from screening in mean, and response distribution of the 5 components of the NOSE Scale score (nasal congestion, nasal blockage, trouble breathing, trouble sleeping, and getting enough air during exercise) at the 3-, 6-, 12-, 24- and 36-month follow-up evaluations.
- Proportion of responders based on improvement in NOSE Scale score at the 3-, 6-, 12-, 24- and 36-month follow-up evaluations.

Visual Analog Scale (VAS) for nasal pain - perception of pain associated with the procedure on a 0 to 100 mm scale (0 indicating no pain and 100 indicating the worst pain ever) assessed immediately after treatment and at 1 week.

Numerical Rating Scale (NRS) for ease of breathing through the nose - perception of the ability to breathe through the nose over the past week on a 0 to 10 scale (0 indicating no difficulty and 10 indicating severe difficulty) assessed at screening, 3, 6, 12, 24 and 36 months.

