4.2 Secondary Objective

The secondary objective is to evaluate the durability of the treatment effect in an extended follow-up period of 36 months.

In addition to the primary and secondary endpoints, both the primary and secondary objectives will be supported by assessment of several other effectiveness and safety measures that will include:

- Adverse events - Incidence (type and category) of adverse events overall and by follow-up interval.
- Nasal Assessment - The target SSB within each nostril will be visually assessed at screening, prior to the procedure, immediately after the procedure, and 3 months after the procedure. The use of an endoscope for visual assessment is required. Representative endoscopic video of each nasal passage will be captured for each assessment. Endoscopic nasal assessment will include assignment of an SSB grading score.³⁶
- CT Assessment – A subset of study sites will be selected to participate in a substudy of the use of CT imaging to assess changes in the SBB after treatment. Radiographic changes, including change in size of the SSB, will be assessed using CT imaging prior to the procedure and at 3 months after the procedure.
- NOSE Scale score:
 - Mean and mean change from screening at the 3-, 6-, 12-, 24- and 36-month follow-up evaluations.
 - Distribution of NOSE Scale score severity categories (mild, moderate, severe, extreme) at the 3-, 6-, 12-, 24- and 36-month follow-up evaluations.
 - Mean, change from screening in mean, and response distribution of the 5 components of the NOSE Scale score (nasal congestion, nasal blockage, trouble breathing, trouble sleeping, and getting enough air during exercise) at the 3-, 6-, 12-, 24- and 36-month follow-up evaluations.
 - Proportion of responders based on improvement in NOSE Scale score at the 3-, 6-, 12-, 24- and 36-month follow-up evaluations.
- Visual Analog Scale (VAS) for nasal pain - perception of pain associated with the procedure on a 0 to 100 mm scale (0 indicating no pain and 100 indicating the worst pain ever) assessed immediately after treatment and at 1 week.
- Numeric Rating Scale (NRS) for ease of breathing through the nose - perception of the ability to breathe through the nose over the past week on a 0 to 10 scale with 0 indicating no difficulty and 10 indicating extreme

Clinical Study Protocol – SWELL Study

difficulty assessed at screening and the 3-, 6-, 12-, 24- and 36-month follow-up evaluations.

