5.4.4 Visual Analog Scale (VAS) for Nasal Pain

A horizontal 100 mm VAS⁴⁵ anchored on the left with the words "No Pain" and on the right with the words "Worst Pain Imaginable", will be used to measure nasal pain associated with the procedure. Scores are obtained by measuring the distance in millimeters from the left origin of the line (0) to the point indicated with a vertical slash placed by the participant to indicate their current level of pain in and around the nose.

5.4.5 Ease of Breathing Through the Nose – Numeric Rating Scale (NRS) Breathing Score

Participants will be asked to describe their perception of their ability to breathe through the nose over the past week on a NRS from 0 to 10 where 0 is defined as "No Difficulty Breathing" and 10 is defined as "Extreme Difficulty Breathing".

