6.1 Schedule of Events

Activity / Assessment	Screening	Treatment			Follow-up (in-office)		Extended Follow-up (remote)			
		Preprocedure	Procedure	Immediate Postprocedure	1 Week	3 Months (13 weeks)	6 Months (26 weeks)	12 Months (52 weeks)	24 Months (104 weeks)	36 months (156 weeks)
Window (days)	(-30)	(0)		(± 3)	(± 14)	(± 30)	(± 30)	(± 30)	(± 30)	(± 30)
Eligibility	X									
Consent	X									
Demographics / Medical History	X									
Physician Evaluations										
Nasal Assessment (visual, endoscopic)	X	X ¹		X	X	X				
CT imaging of SSB	X ²					X				
Current medication use (study relevant)	X			X ³	X	X	X	X	X	X
Participant Evaluations										
NOSE Scale	X ⁴					X ⁵	X	X	X	X
VAS nasal pain				X	X					
NRS ease of breathing	X					X	X	X	X	X
Participant Satisfaction Survey						X	X	X	X	X
SNOT-22	X					X	X	X	X	X
Study Procedure (includes anesthesia)			X							
Adverse Events	X			X	X	X	X	X	X	X

¹ Nasal Assessment do not need to be repeated if Screening and Treatment visits occur on the same day.

[figure not shown]
² CT should only be performed if your site was selected for the CT substudy and only after all other screening procedures and participant eligibility is confirmed.

³ Add any postprocedure medications to the medication log.

⁴ Baseline NOSE Scale Score for analysis is defined as the Screening score.

⁵ Primary analysis endpoint evaluation.

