- Proportion of responders based on improvement in NOSE Scale score at the 3-, 6-, 12-, 24- and 36-month follow-up evaluations for each group.
- VAS for nasal pain- Summary will include mean NRS pain scores assessed postprocedure.
- NRS for ease of breathing - Summary will include mean and mean change from baseline (screening) of ease of breathing scores assessed at screening and at each follow-up evaluation.
- SNOT-22 - mean and change from baseline (screening) in mean SNOT-22 score and individual domain scores will be summarized at the 3-, 6-, 12-, 24- and 36-month follow-up evaluations.
- Participant Satisfaction Assessment - mean response for each of the 5 survey questions will be summarized at the 3-, 6-, 12-, 24- and 36-month follow-up evaluations.
- Medications - Medication, and other therapies associated with relief or treatment of NAO symptoms will be documented at screening and updated as necessary with changes to any treatment and any new associated medications at each postprocedure evaluation. An increase or decrease in frequency of use or dose, no change, starting new or stoppage of medication use compared to the first recorded use will be documented.

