9.3.2 Case Report Forms

Standardized electronic case report forms (eCRFs) will be used at all participating study sites to collect complete and accurate records of the clinical data. All study data will be entered by study personnel through eCRFs for each participant screened in the study. A unique ID number will be assigned to each participant.

The following eCRFs and logs will be used in this study and submitted at the intervals outlined in Table 1:

- Screening Visit / Study Eligibility (01)
- ICF Checklist (01A)
- Screening Visit – Demographics, Treatment History & Nasal Exam (02)
- CT Settings Checklist (02A) (selected sites only)
- NOSE Scale (03)
- NRS Ease of Breathing– Participant form (04)
- SNOT-22 (05)
- Preprocedure (06A)
- Anesthesia and Procedure (06B)

Clinical Study Protocol – SWELL Study

- Immediate Postprocedure (06C)
- VAS for nasal pain – Participant form (07A)
- VAS for nasal pain – Site form (07B)
- Follow-up Visit (08)
- Participant Satisfaction Survey (09)
- Study Exit (10)
- Device Malfunction Report (11)
- Protocol Deviation (12)
- Adverse Event Report (13A) (reference AE Code List [13B])
- Serious Adverse Event / Unanticipated Adverse Device Effect (SAE / UADE) Report (14)
- Medication Log (15)
- Unscheduled Visit (16)

Clinical Study Protocol – SWELL Study

Table 1. Schedule of case report forms and related materials.

Visit	Visit Window (days)	eCRF	Other
Screening	n/a	01, 01A, 02, 02A*, 03, 04, 05, 15	Informed Consent Nasal assessment images [†] CT imaging*
Study Procedure (preprocedure/anesthesia/treatment)	within 30 days of Screening	06A, 06B,	Nasal assessment images [†] Nasal assessment does not get repeated Preprocedure if the Screening and Treatment visits occur on the same day
Postprocedure	0	06C, 07A, 07B, 15	Nasal assessment images [†]
1-Week (In-office)	+3	07A, 07B, 08, 15	Nasal assessment images [†]
13-Week (In-office)	±14	02A*, 03, 04, 05, 08, 09, 15	Nasal assessment images [†] CT imaging*
6-Month (Remote)	±30	03, 04, 05, 08, 09, 15	
12-Month (Remote)	±30	03, 04, 05, 08, 09, 15	
24-Month (Remote)	±30	03, 04, 05, 08, 09, 15	
36-Month (Remote)	±30	03, 04, 05, 08, 09, 10, 15	
As Needed	n/a	10, 11, 12, 13A, 13B, 14, 16	

[†]Copy de-identified endoscopic video/images collected for study records to USB flash drive and provide to Sponsor.

*Sites selected for substudy only

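### The 1-week pain VAS has no pretreatment reading, so any nasal pain already present would be counted as procedural pain

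*Combined protocol and SAP*

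**What the plan says.** **Purpose.** Section 5.4.4 says that the VAS "will be used to measure nasal pain associated with the procedure". The Protocol Summary describes it as "perception of pain associated with the procedure on a 0 to 100 mm scale", and Section 4.2 places it at two times: "assessed immediately after treatment and at 1 week". Both readings carry the procedural label.

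**What is marked.** Section 5.4.4 has the participant place a slash "to indicate their current level of pain in and around the nose". Section 6.5 gives the immediate reading a different instruction, asking for the pain felt between the start of anesthesia and the end of the procedure. Section 6.6 lists the 1-week item only as "VAS for pain score (completed by participant", with no recall period and no attribution.

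**When it is taken.** In Section 6.1 the row "VAS nasal pain" is marked at Immediate Postprocedure and 1 Week only. The screening assessments in Section 6.3 do not include it. In Table 1 (Section 9.3.2) the screening forms are "01, 01A, 02, 02A*, 03, 04, 05, 15"; the VAS forms 07A and 07B first appear at Postprocedure and again at 1 week.

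**How it is analyzed.** Section 7.12 says: "Summary will include mean NRS pain scores assessed postprocedure". No change score is planned, and the instrument is called an NRS.

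**The concern.** A score of current nasal pain at 1 week is the sum of whatever the procedure left behind and whatever was there before. With no pretreatment VAS and no control arm, the score alone cannot separate the two, yet the plan's label assigns all of it to the procedure.

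This matters modestly for the tolerability description. Section 8.1.2 does not require pain that is part of normal recovery to be reported as an adverse event, so the 1-week VAS is the only millimeter-scale pain record after discharge. The plan treats its other participant-reported scores differently: NOSE, the breathing NRS and SNOT-22 all have a screening value and a planned change from it.

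**Working it through.** The plan states no figure for this outcome, so there is none to reproduce. The check is a comparison of the text, followed by an illustration of size.

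**Step 1. Compare the two readings.**

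| | Immediate | 1 week |
|---|---|---|
| Label (Summary, 4.2, 5.4.4) | procedural pain | procedural pain |
| Question described | pain during the procedure (6.5) | current nasal pain (5.4.4); 6.6 adds nothing |
| Tied to the procedure by its wording | yes | no |
| VAS before treatment | none | none |
| Planned summary (7.12) | raw mean | raw mean |

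The immediate reading needs no baseline, because its question limits it to the procedure. For the same reason it cannot serve as a baseline for 1 week: it records a different quantity. The gap is confined to the 1-week score.

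**Step 2. Look for another pretreatment pain measure.** The nasal assessment in Section 5.4.1 includes a four-level soreness/pain grade. Sections 6.1 and 6.6 have the assessment done at screening, before the procedure (not repeated if screening is the same day), immediately after, at 1 week and at 3 months. So a same-scale record exists before treatment and at 1 week. It is not in millimeters, no rule links it to the VAS, and Section 7.12 omits 1 week from the time points at which the assessment components are summarized.

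**Step 3. Size.** Let q be the share of participants with nasal pain before treatment and m their mean pain in mm that persists at 1 week. If background and procedural pain add, then

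observed 1-week mean = procedural mean + q × m,

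so the bias is q × m. The documents give neither q nor m. Assumed values:

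| q | m (mm) | q × m (mm) |
|---|---|---|
| 5% | 10 | 0.05 × 10 = 0.5 |
| 10% | 20 | 0.10 × 20 = 2 |
| 20% | 20 | 0.20 × 20 = 4 |
| 30% | 30 | 0.30 × 30 = 9 |

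The bias cannot be negative, so it overstates procedural pain. It is zero if nobody has pain beforehand or if none of it persists.

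**The case against.** **Nothing shows that these participants have nasal pain.** Entry rests on obstruction. The symptoms listed in Section 1.0 do not include nasal pain, and neither do the five NOSE components. This stands. Sections 5.2 and 6.3 anticipate prior nasal surgery in many participants and record any history of rhinitis, sinus disease or nasal trauma. That makes some background pain plausible, but no more. A reader might infer that the 1-week mean is in fact inflated, perhaps by 5 to 15 mm across the cohort; the documents do not support this. An average of 15 mm would need, for example, half the participants with 30 mm of persisting pain (0.50 × 30 = 15).

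**The soreness/pain grade already covers it.** This stands in part. A reader might infer that the plan has no way to find participants whose pain rose. That is too strong: a move up the four-level grade between pretreatment and 1 week identifies them coarsely. What is missing is a planned table, and a baseline on the VAS scale.

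**The prompt on form 07A is not reproduced.** It may itself ask about procedural pain, in which case the question makes the attribution. That is possible, but Section 5.4.4 is the only description of the mark that applies at 1 week, and it says current pain. The uncertainty is a reason to reconcile the wording.

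**Little depends on it.** This stands. Section 7.12 classes the measure as informational and hypothesis-generating. It enters neither hypothesis in Section 7.2, nor the success criterion in Section 5.5.2, nor the safety endpoints in Section 7.11, and any bias runs against the device.

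**Conclusion.** The point holds in a conditional form. As described, the 1-week VAS measures current nasal pain, is reported as procedural pain, and has no pretreatment value to subtract; any persisting background pain would be counted as procedural. The size is unknown. The illustrative range of 0.5 to 9 mm rests on assumed shares and pain levels, on additivity, and on the pain persisting to 1 week. The immediate reading and the primary and secondary endpoints are unaffected. This is a worthwhile, low-cost improvement to a descriptive outcome and does not threaten the study's conclusions.

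**What to change.** 1. **Collect.** Add forms 07A and 07B to the Preprocedure column in Section 6.1, to the preparation step in Section 6.4 and to Table 1. The participant completes the VAS before any decongestant, endoscopy or anesthetic that day. Specifying only that it precede the anesthetic is not enough: screening and treatment may share a day, and the screening endoscopy and the decongestant test on the swell body would then come first.
2. **Analyze.** In Section 7.12, report the within-participant VAS change from Day 0 to 1 week beside the 1-week mean, with the number whose score rose. Add 1 week to the summary of the soreness/pain grade, with its shift from pretreatment. Correct the reference to NRS pain scores to VAS.
3. **Reconcile the wording.** Align Sections 5.4.4 and 6.5 with the form so that the pretreatment and 1-week readings both ask for current pain, and the immediate reading is identified as a separate question about pain during the procedure.

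If enrollment is already complete, item 1 is no longer available. The 1-week result can then be labeled as current nasal pain and tabulated by the pretreatment soreness/pain grade, which uses data already collected.

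**Cost.** One extra participant-completed line on Day 0 on an existing form, and one or two table rows. No added visit or staff.

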5.5.1 Participant Success

The primary outcome success measure for a participant in this study is based on an improvement (decrease) in the NOSE Scale score after the procedure compared to the baseline (screening) score. The improvement must reflect at least one category improvement or $\geq 20\%$ decrease in score at the 3-month evaluation for the participant to be considered a success (responder). A participant will be considered a nonresponder (failure) at the 3-month evaluation if neither success criterion has been attained.

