7.6 Missing Data

Every effort will be made to obtain complete follow-up data for all participants, and it is anticipated that analysis of the primary and secondary endpoint hypotheses will be conducted using all available complete data. The effect of missing data will be examined by imputing missing NOSE scores as no change from baseline and as nonresponders.

Other outcome measures will be analyzed by using available data only.

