8.1.2 Documentation and Reporting of Adverse Events

All adverse events will be monitored from the time of study entry through study exit. All adverse events must be reported on the Adverse Event Report eCRF. A description of the event, including onset date, resolution date, action taken, and the outcome should be provided. All adverse events will be followed until they are adequately resolved or reach a chronic, stable state. If a participant reaches the 36-month follow-up visit and is experiencing a new or ongoing adverse event, the sponsor should be contacted to discuss the need and/or methods for continued surveillance of the event. Adverse events will be evaluated by the investigator and differentiated by:

- Seriousness
- Intensity (mild, moderate, severe)
- Causality (in relation to the device or procedure)
- Unexpectedness

Signs and symptoms considered normal postprocedure recovery (eg, postprocedure pain, transient sensory symptoms, fever, postanesthesia symptoms) do not have to be reported as adverse events. If these events require treatment outside that which is considered normal or if the event lasted longer in duration than normal, they should be reported as adverse events.

All adverse events classified as an Unanticipated Adverse Device Effect, Serious Adverse Device Effect, or Serious Adverse Event must be reported to the sponsor within 24 hours of learning of the event.

Sponsor Contact: [name]

[contact]

Email: [contact]

Clinical Study Protocol – SWELL Study

Investigators must also report promptly all unanticipated problems to their IRB/EC and/or regulatory authority involving risks to participants or others and report adverse events according to the local or national reporting requirements. Reporting instructions and contact information will be provided in the site's Regulatory Binder for this study.

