10.6 Participant Withdrawal

Participants may voluntarily withdraw from the study at any time for any reason without impact to their future medical care at the study site. In addition, the investigator may withdraw a participant from the study, if in the investigator's opinion, it is not in the best interest of the participant to continue in the study. Any participant withdrawing from the study for any reason will continue to receive medically necessary follow-up care as determined by the investigator. Every attempt should be made to follow a participant withdrawing either because they failed to obtain a desired effect or suffered an adverse event.

When a participant chooses to withdraw, the investigator or designee will make all possible efforts to collect and report the final visit observations. If the investigator has made 3 documented attempts to contact the participant and received no response, the participant may be considered to be lost to follow-up. A participant who misses a study visit but attends a subsequent visit will no longer be considered lost to follow-up. All reasons for withdrawals and documentation will be recorded in source documentation and the appropriate case report form. In addition, within the informed consent process, participants will be asked to provide consent for the study staff to contact them by mail or phone to follow up on safety-related issues as appropriate.

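### Section 6.6 lets a physician's exit decision end data collection before week 13, against 6.5, 10.6 and 6.6 itself, while 7.6 tests both efficacy hypotheses on complete data

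*Combined protocol and SAP*

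**What the plan says.** Under Study exit, section 6.6 states: "Study exit applies to those participants where data is no longer collected for a study participant". Its list of exit cases includes "Physician exited participant based on medical or surgical necessity or other reason", and next to it treatment received outside the study that, in the investigator's opinion, would affect the results. Neither item has criteria or a time limit.

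Other text points the other way:

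- Section 6.6, earlier: "All participants should be followed through the final follow-up evaluation at 156 weeks (36 months) postprocedure regardless of their earlier success/failure classification".
- Section 6.5: a participant given another treatment or procedure in their best interest stays in the study and is followed to 36 months.
- Section 10.6: the investigator may withdraw a participant when continuing is not in that participant's best interest. It adds: "Every attempt should be made to follow a participant withdrawing either because they failed to obtain a desired effect or suffered an adverse event". It also asks for final visit observations.

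On analysis, section 7.6 says "it is anticipated that analysis of the primary and secondary endpoint hypotheses will be conducted using all available complete data". The effect of missing data is then examined by imputing no change from baseline and nonresponse.

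On forms, the As Needed row of Table 1 (9.3.2) lists "10, 11, 12, 13A, 13B, 14, 16". That includes Study Exit (10) and the Adverse Event Report (13A), but not the NOSE Scale (03) or the Follow-up Visit form (08).

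On safety, section 8.1.2 says "All adverse events will be monitored from the time of study entry through study exit", and also that adverse events are followed until resolved or stable.

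**The concern.** The procedure is given once, on Day 0, and repeat procedures are not allowed. Leaving the study therefore cannot stop treatment; it can only stop measurement. The listed reasons (medical or surgical necessity, outside treatment, anything else) are plausibly related to poor response or harm. They are applied by the treating physician, who knows the treatment, in a single-arm study with no comparator to share the bias.

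A participant exited before week 13 has no 13-week NOSE score and drops out of the analyses that decide both hypotheses. If such exits are mainly failures, the mean change and the responder percent are both too favourable. If the sensitivity analysis then disagrees, the plan does not say which conclusion stands.

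There is also a narrower safety gap. An adverse event that first arises after exit but before month 3 may go uncollected, although the serious adverse event endpoint runs through 3 months.

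**Working it through.** **Passages side by side**

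| Situation | Text that ends collection | Text that continues it |
|---|---|---|
| Physician decides on exit | 6.6 exit list, any reason | 10.6, best-interest test only, with continued attempts to follow failures and adverse-event withdrawals |
| Outside treatment | 6.6 exit list, investigator's opinion | 6.5, stays in the study to 36 months |
| Treatment failure | 6.6 exit list, if the physician so decides | 6.6, follow to 156 weeks regardless of success or failure |

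The outside-treatment row is the plainest contradiction: a site cannot apply both rules to the same participant.

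**Inputs.** From 7.3: n = 70, one-sided alpha 0.025, SD of change 20, expected change -50 against a threshold of -25, and expected response 0.80 against 0.55. From 7.11: a binomial test, met if the lower 95% bound exceeds 0.55. The interval method is not named; exact (Clopper-Pearson) is assumed here. The documents give no exit rate, so the number of exits k is assumed. All exits are taken as nonresponders, or as having zero change.

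**The plan's own figures.** Paired t-test, noncentrality (25/20) × √70 = 10.46: power above 0.999. Exact binomial, at least 48/70 needed: power 0.992 at 0.80, actual alpha 0.014. The stated 0.99 is reproduced for the responder endpoint and is conservative for the primary.

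**Responder verdict.** The smallest count r with P(X ≥ r | n, 0.55) ≤ 0.025 is 48 for n = 70, 45 for n = 65 and 43 for n = 63.

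- k = 5: 45/65 = 69.2%, lower bound 56.6%, passes. With the exits counted as failures, 45/70 = 64.3%, lower bound 51.9%, does not pass. The verdict differs for 45 to 47 responders.
- k = 7: it differs for 43 to 47.

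**False success if the true all-treated response is exactly 0.55 and k nonresponders exit:**

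| k | Complete data | Exits counted as nonresponders |
|---|---|---|
| 0 | 0.014 | 0.014 |
| 2 | 0.045 | 0.014 |
| 4 | 0.074 | 0.014 |
| 7 | 0.168 | 0.014 |

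**Primary verdict, k = 5.**

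- Complete data, n = 65: the margin is 1.998 × 20/√65 = 4.96, so the test passes at an observed mean of -29.96 or better.
- With 5 zeros added and a completer mean of -M, the mean over 70 is -65M/70 and the variance is [64 × 400 + (65 × 5/70)M²]/69. At M = 32.3 the mean is -30.0, the SD is 21.0 and the margin is 1.995 × 21.0/√70 = 5.0, which just passes.
- The verdict therefore differs only for an observed completer mean between about -30.0 and -32.3.

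**At the planned values.** A completer mean of -50 becomes -50 × 65/70 = -46.4. The reported effect shrinks by 3.6 points and the primary verdict does not change. The probability of 45 to 47 responders at 80% response is about 0.7% if the 80% applies to all 70, and about 7% if it applies to 65 completers.

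**The case against.** The exit item is one entry in a list of occasions for completing a form. It mentions neither week 13 nor failure. The withdrawal authority is in 10.6 and is narrower. Sections 6.5, 6.6 and 10.6 all tell sites to keep following people, 7.6 already plans a conservative imputation, and 7.8 reports withdrawals and exclusions with reasons, so selective exit would be visible. This stands to the extent that selective exit is a possibility and not a stated rule. It does not remove the contradiction, because 6.6 itself says that data are no longer collected after exit. Nor does it supply a rule for the case in which the two analyses disagree.

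Two stronger readings are tempting, and the documents do not support them.

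- A reader might infer that harmed participants disappear from the 3-month safety results. They do not. Section 7.5 puts all enrolled participants in the safety population, events before exit count, 8.1.2 follows known events until resolved or stable, and 7.14 requires narratives for withdrawals due to an adverse event. Only new events between exit and month 3 are at risk.
- A reader might infer that 5.5.1 flatly contradicts 7.6, since 5.5.1 says "A participant will be considered a nonresponder (failure) at the 3-month evaluation if neither success criterion has been attained". That sentence classifies participants at the 3-month evaluation and need not cover someone who has no such evaluation. The conflict is one reading only.

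Making imputation the sole deciding analysis would also be a trade-off and not a correction: if 7 exits were unrelated to outcome, counting them as nonresponders would lower power from 0.991 to 0.821.

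**Conclusion.** The point holds as an internal contradiction with a statistical consequence. The exit list in 6.6 must be reconciled with 6.5, 10.6 and the follow-up rule in 6.6. Until it is, outcome-related exits before week 13 can bias both efficacy results in favour of the procedure, and the plan does not say what is concluded if the imputed result disagrees.

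The size depends on assumed exits that are all failures. With 5 of 70, the verdict changes only in a narrow band: 45 to 47 responders, or a mean change of about -30.0 to -32.3. If the planned effects are realised, the primary conclusion is safe and a changed responder conclusion is unlikely. The bias matters most if the true effect is near the thresholds. The change should be made, but the point does not by itself invalidate the design.

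**What to change.** 1. Reconcile 6.5, 6.6 and 10.6. Delete the open-ended last words of the physician-exit item. For treated participants, let a physician decision or outside treatment end study visits but not collection of the 13-week NOSE score and adverse events. That collection should stop only for withdrawal of consent, death or loss of contact.
2. In Table 1, schedule forms 03 and 08 at week 13 for these participants; 13A is already available as needed. Make sure the consent covers this contact, because the contact consent described in 10.6 is limited to safety-related issues.
3. In 7.6, apply the existing no-change and nonresponder imputation to every treated participant without a 13-week NOSE score. Do not restrict it to exits coded by reason, since the unmasked investigator assigns the code. Report the result beside the complete-data result, and state that success is not claimed without qualification if the two disagree.

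The cost is protocol and consent wording, a few extra contacts, and possibly a slightly less favourable estimate.
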